Official Title:

A Randomized, Controlled, Multicenter Trial of Percutaneous Peripheral Nerve Stimulation (PNS) for the Treatment of Back Pain

NCT#: 04246281

Date: 4 April 2024

A Randomized, Controlled, Multicenter Trial of Percutaneous Peripheral Nerve Stimulation (PNS) for the Treatment of Back Pain

Sponsor: SPR™ Therapeutics, Inc.
[name]
[name]
[name]

Study Device: SPRINT® PNS System

FDA Clearance for SPRINT® PNS System: K181422; K202660, K211801, K223306

Initial Date and Version: [REDACTED]

Amendments Dates/Versions: [REDACTED]

[figure not shown]
4 April 2024

Confidential Information:

This protocol contains confidential information for use by the Investigator and their designated representatives participating in this clinical investigation. It should be held confidential and maintained in a secure location. Do not copy or distribute without permission.

Protocol Synopsis

Title	A Randomized, Controlled, Multicenter Trial of Percutaneous Peripheral Nerve Stimulation (PNS) for the Treatment of Back Pain
Study Nickname	The RESET Clinical Trial
Device (510k Cleared)	The SPRINT® Peripheral Nerve Stimulation (PNS) System
Study Design	Prospective Randomized, Controlled, Multicenter Post Market Study
Primary Study Objective	The objective of the proposed study is to compare the effectiveness of percutaneous PNS to standard interventional management for the treatment of back pain. [REDACTED]
Study Plan	
Individuals must have an average pain intensity score of ≥ 4 out of 10 to qualify. Individuals who report chronic low back pain confined to the lower back will be considered for enrollment into the study. After obtaining informed consent, potential subjects will be evaluated for general eligibility. To qualify for enrollment in the study, individuals must report average pain intensity in the previous week of ≥ 4 out of 10 (Brief Pain Inventory-Short Form, Question #5). Subjects must have failed at least 2 previous types of LBP therapies (e.g., medications, physical therapy, injections) to participate.
 
Subjects will be randomized into one of two groups: Treatment with SPR's percutaneous PNS System (Group #1) or Control, treatment with conventional management (e.g., using radiofrequency ablation (RFA) or other standard interventional management, Group #2. The individuals who satisfy the preliminary criteria will be asked to complete a 7-day baseline diary to record their daily "average pain" intensity (Question #5 on the BPI-SF). Individuals must report an average pain intensity of ≥ 4 averaged across the 7-day diary to qualify to continue participation. Subjects randomized to Group 1 will undergo a diagnostic medial branch block (MBB) and regardless of the results, will then receive peripheral nerve stimulation (PNS) via two fine-wire leads placed percutaneously to activate nerves innervating muscles of the lower back and connected to an external pulse generator PNS parameters will be adjusted to produce comfortable sensations and subjects will be instructed to use stimulation daily for eight weeks. Subjects randomized to Group 2 will receive standard treatment of care (e.g., lumbar radiofrequency ablation, spinal cord stimulation, surgery, etc) following diagnostic testing or procedures, as appropriate (e.g., diagnostic MBB). After 8 weeks of PNS, subjects in Group 1 will return to the clinic to have their lead(s) removed. Subjects in Group 2 are eligible to crossover to receive SPRINT and continue study participation after 12 months. The

	
primary endpoint will be assessed at 3 months after treatment with PNS or standard interventional management.
 
Average pain intensity will be measured for up to 24 months following treatment. Subjects will use numerical rating scales to record average pain intensity (BPI-5) and worst pain intensity (BPI-3) over the past 24 hours, and record daily analgesic medication usage each week at baseline, 1-, 2-, 3-, 6-, 9-, 12-, 18- and 24-months after treatment. The study will compare the efficacy of percutaneous PNS for the treatment of chronic low back pain to standard interventional management for the treatment of chronic low back pain, by evaluating if the treatment effect is equivalent (i.e., statistically non-inferior), and if so, if it is superior.
 
Sites (N)	Up to 30 sites
Subjects (N)	Up to 230 individuals will be randomized
Inclusion Criteria	
 • Age \geq 21 years and \leq 75 years • Able to understand and comply with study requirements and provide written informed consent • Chronic low back pain (i.e., pain lasting longer than 6 months, where the vast majority and center of pain is in the lumbar region, L1-L5 vertebral levels) • Reports an average low back pain score \geq 4 on a scale of 0-10 (BPI-5) • Previous use of at least two types of LBP therapies (e.g., medications, physical therapy, injections, etc.) • At least 4 weeks of stable pain treatment or medication as indicated by subject reported medication history (i.e., no new treatments or change in medication for pain in the last 4 weeks) • Reports active health insurance coverage (e.g., through commercial insurance, Medicare, Medicaid, Tricare)
Exclusion Criteria	
 • Radicular leg pain (e.g., pain that spreads to the lower extremities) or referred pain outside the lumbar region (e.g., sacral pain, hip pain) that is \geq 4 on a scale of 0-10, BPI-5 • Pain in the thoracic or cervical region that is \geq 4 on a scale of 0-10, BPI-5 • Pain from the sacroiliac joint, as determined by the Investigator • Signs of infection on or around the low back, or other conditions that increase risk to the subject in the opinion of the Investigator

	
(e.g., valvular heart disease that creates an infection risk, compromised immune system, history of recurrent skin infections)
 
 • Signs of serious underlying cause of low back pain as determined by the Investigator, (e.g., cancer, chronic infection, referred visceral pain, metabolic bone disorder) • Deep brain stimulation (DBS) system, an implanted active cardiac implant, or any other implantable neurostimulator whose stimulus current pathway may overlap the Sprint Stimulator's current pathway • Anesthetic or corticosteroid injections in the low back (including trigger point, epidural, intrathecal, facet, or sacroiliac joint injections) within the last 3 months (not including a diagnostic medial branch block), or botulinum toxin (Botox) injection in the low back within the last 6 months • Prior radiofrequency ablation of the lumbar medial branches (L1-L5) within the last 6 months • Prior lumbar surgery • Clinically relevant stenosis of the central canal or foramina as determined by the Investigator (e.g., symptoms of neurogenic claudication) • Greater than mild lumbar scoliosis (i.e., > 20 degrees) • Condition that could impact response to percutaneous PNS (e.g., fibromyalgia confirmed by a specialist, multiple sclerosis, spinal cord injury, or other neurological disease or damage to central or peripheral nervous system) • History of significant trauma to the lumbar spine or paraspinal musculature (e.g., burst fractures or fracture dislocations) • Score of > 20 on the Beck Depression Inventory (BDI-II) • Average Pain Interference score < 4 using BPI-9 • Obese with a body mass index (BMI) > 40 • Current illicit substance abuse or high-dose opioid dependence (e.g., daily opioid usage \geq 90 mg morphine equivalents) • Current participation, or less than 30 days from completing any drug or device trial, or previously received SPRINT for LBP • Pending litigation, workers compensation or other secondary gain issues • Tape or adhesive allergy • Allergy to all local anesthetic agents (e.g., lidocaine) • Any other medical condition that may interfere with ability to participate in a clinical trial as determined by the Investigator (e.g., bipolar disorder) • Vulnerable populations (e.g., prisoners, individuals that report to investigators) • Bleeding disorder (e.g., hemophilia)
--	---

Additional Inclusion Criteria	
 • Assessed before randomization: Average pain intensity score of ≥ 4 (determined by calculating the mean “average pain” collected in a 7-day baseline diary, using Question #5 on the BPI-SF)
Additional Exclusion Criteria	
 • Assessed before start of treatment: Pregnancy (Group #1 only)
Primary Safety Endpoint	Occurrence and type of study-related adverse events.
Primary Clinical Endpoint	
Clinically significant reduction in chronic low back pain as evidenced by $\geq 50\%$ reduction in “average pain intensity” (BPI-5) 3 months after start of treatment (i.e., average of weekly diary) compared to baseline (i.e., average of baseline diary).
 
 • The primary endpoint compares the proportion of subjects in Group 1 (PNS) relative to that in Group 2 (Control) that achieve $\geq 50\%$ reduction in average back pain intensity from baseline to 3-month follow up. This endpoint will examine the statistical non-inferiority of the proportion of clinical successes in Group 1 compared to Group 2, and if non-inferiority is achieved, examine the statistical superiority of the proportion of successes in Group 1 compared to Group 2.
Secondary Endpoints	
Several secondary endpoints will be collected to evaluate what effect, if any, the interventions have on each measure. Unless specified, secondary efficacy endpoints for the following outcome measures will be assessed at 3 months after start of treatment.
 
 • Proportion success evidenced by 30% reduction in pain interference as measured using Question #9 of the BPI-SF (BPI-9) compared to baseline • Proportion with clinically significant change (≥ 10-point reduction) in disability as measured using the Oswestry Disability Index (ODI) compared to baseline • Durability of primary endpoint (proportion success with 50% reduction in average back pain intensity) at 6- to 24-months after treatment • Proportion success with 50% reduction in worst back pain intensity as measured using Question #3 of the BPI-SF (BPI-3) compared to baseline • Average Patient Global Impression of Change (PGIC) • Average change in health-related quality of life as measured using the EQ-5D compared to baseline • Average change in analgesic medication usage

Exploratory
Measurements

[figure not shown]

Table of Contents

Protocol Synopsis	2
1.0 GENERAL INFORMATION	9

1.0 GENERAL INFORMATION

1.1. Title of the Investigation

A Randomized, Controlled, Multicenter Trial of Percutaneous Peripheral Nerve Stimulation (PNS) for the Treatment of Back Pain

1.2. Study Nickname

In addition to the formal study title above, this trial may also be referred to as The RESET Clinical Trial. Additional variations on this nickname may include The RESET RCT and The RESET Low Back Pain Study.

1.4. Name of the Device

The SPRINT® Peripheral Nerve Stimulation (PNS) System

1.5. Indication for Use

1.6. Study Objective

The objective of the proposed study is to compare the effectiveness of percutaneous PNS to standard interventional management for the treatment of back pain.

2.0 BACKGROUND AND JUSTIFICATION FOR THE DESIGN OF THE CLINICAL INVESTIGATION

Chronic LBP is a substantial medical problem

Chronic LBP is a substantial medical problem and a growing socioeconomic burden (1). Chronic LBP affects approximately 10% of the U.S. population and is the second leading cause of disability (2). Chronic LBP is associated with reduced activities of daily living, reduced quality of life, and a cost of \$100-200 billion/year in the U.S. for treatment, missed workdays and reduced productivity (3-5). LBP has a global prevalence of approximately 12% and is likely to increase substantially in the future as the population ages (6). Further,

the direct medical costs associated with LBP represent only a small portion of the total costs of LBP, suggesting that therapies that reduce disability may also offer significant societal cost savings (1), in addition to improvements in quality of life for the individuals.

Acute LBP is characterized as pain lasting 3-6 weeks and usually resolves, although pain recurrences are common after the initial episode of acute LBP (7). Chronic LBP lasts > 12 weeks and is typically associated with greater pain intensity scores and bilateral pain (as opposed to unilateral or radiating pain) (8), and may be complicated by psychosocial dysfunction (9). Chronic low back pain is confined to pain in the low back area and usually caused by anatomical lesions (e.g., degenerated or herniated intervertebral discs) or damage to soft tissues (e.g., muscles, ligaments, or tendons).

Other treatments for chronic low back pain are ineffective, not well tolerated or associated with side effects and complications

Analgesics: Oral medications (e.g., acetaminophen, NSAIDs, muscle relaxants, tricyclic antidepressants, antiepileptics, corticosteroids) provide only limited and/or short-lived pain relief, and typically produce side effects (e.g., sedation, gastrointestinal problems) (10, 11). Although analgesics can provide substantial pain relief in some (52-55% of patients fail to experience sufficient pain relief (12, 13)), long-term use is not recommended (e.g., to prevent opioid dependence (11)).

Physical Therapy or Exercise: Physical therapy (PT), including strength training, may be capable of targeting both the physical dysfunction and pain. Exercise (including yoga, stretching, strength training) has a low level of risk and can relieve pain and improve function long-term, but patients often fail to comply with treatment regimens due to discomfort, lack of motivation, and inconvenience (14, 15). Studies have shown that when subjects are motivated and compliance is high with PT or exercise, chronic LBP and disability are significantly reduced, which is why PT is a common first-line therapy and currently the standard of care (16, 17). Unfortunately, many patients generally fail to comply with prescribed treatment regimens (14, 15) ($\geq 50\%$ have poor compliance attending PT sessions or completing home exercises (18)), resulting in a return of pain and dysfunction (19) and the need for an alternative first-line treatment for pain specialists to provide for chronic LBP.

Physical manipulation: Physical manipulation (e.g., massage, spinal manipulation) has a low level of risk and can provide short-term pain relief (20, 21). However, frequent treatment sessions are required to maintain pain relief, which is expensive and inconvenient for patients (22). Further, clinical studies on physical manipulation treatments have been poorly controlled.

Injections: Injections of steroids or anesthetic provide short-term pain relief but do not produce long-term benefit. As well, injections produce side effects and complications, including increased pain, lightheadedness, headache, infection, and nausea and vomiting (23-25).

Acupuncture: Acupuncture is minimally-invasive, and studies have suggested that acupuncture can provide pain relief and improvements in function (26). However, the adequacy of sham (placebo) controls in acupuncture studies has been questionable, and the effectiveness of acupuncture remains controversial (27).

Intrathecal Therapy: Intrathecal drug delivery is effective for reducing pain and improving function long-term (28) but requires an invasive procedure and is limited by a host of frequent side effects (e.g., nausea, infection, intrathecal granuloma) (29). Also, technical complications (i.e., problems with catheter or pump) are common and may require reoperation or removal of the device (30).

Surgery: Surgical procedures for back pain (spinal fusion, disc replacement) have become a common treatment of chronic LBP following failure of nonsurgical pain management (Munoz et al. 2016). Fusion is controversial, but has been found to be more efficacious than nonsurgical care in some cases of chronic intractable back pain (Hagg 2003, Fritzell 2005). However, alternative treatments are needed because surgery is highly invasive, irreversible, and carries risks of complications (31, 32) and frequently requires reoperation (31-33). Other types of back surgery (e.g., laminectomy, spinal decompression, discectomy) are typically indicated for radicular pain.

[figure not shown]
[figure not shown]
Transcutaneous electrical nerve stimulation (TENS): TENS has been investigated as a method of relieving chronic LBP (34). Although TENS is a widely accepted method of relieving some types of pain, there is limited evidence that it is effective at relieving chronic low back pain (35-37). In addition, stimulation intensity during TENS is often limited due to the activation of cutaneous nerve fibers, which can cause discomfort and irritation. Because stimulation intensity is limited during TENS, the therapy delivered may be suboptimal.

Radiofrequency Ablation (RFA): Lumbar RFA is a commonly used intervention for the treatment of chronic axial low back pain. RFA uses high frequency electrical current to ablate or lesion nerves to stop transmission of pain signals. In the low back, RFA is commonly performed on the medial branch of the dorsal ramus, which innervates the facet joints, paraspinal muscles, and skin of the low back. RFA can provide months of relief in properly selected patients (e.g., those receiving significant pain relief from diagnostic anesthetic injections or medial branch blocks), but results are highly dependent on physician expertise and approach, and are often followed by an eventual return of pain (38). Further, the destruction of nerves and recurrence of pain is a significant concern for younger populations suffering from chronic low back pain (i.e., military service members, athletes).

Spinal cord stimulation (SCS): SCS has long been investigated for the treatment of low back pain (39), but successful pain relief varies greatly with back pain category and across different studies. SCS parameters can be difficult to program for sufficient pain relief (40) and SCS is historically less effective for predominant back pain than leg pain (41, 42). SCS is associated with complications following the invasive stimulation implant procedure, up to 43% of patients reported complications (43) and reoperation is often

required to reposition the lead, or for other technical complications, including damage to the lead or system failure (29, 44, 45). Because of the invasiveness, cost, and risk of device- and procedure-related complications, SCS is often reserved as a treatment of last resort.

Other Therapies: Other therapies (laser therapy, orthotics, thermal therapies, traction, ultrasound, lidocaine patch) are only useful for mild or non-chronic (<12 weeks) pain, controversial, and/or investigational.

Summary

Chronic low back pain is a significant problem and other current therapies for treatment are ineffective or associated with side effects and complications. Percutaneous peripheral nerve stimulation (PNS) has been shown to relieve LBP, while improving disability and quality of life. The proposed study will determine if the safety and effectiveness of percutaneous PNS is equivalent (and if so, if it is superior) to that of standard interventional management and determine if PNS produces clinically significant

reductions in back pain, disability, and other key patient-centric outcomes.

3.0 DEVICE DESCRIPTION

This study utilizes the commercially available SPRINT® PNS System.

3.1. System Component Overview

4.0 STUDY DESIGN

4.1. General Overview

This study is a post-market randomized controlled trial to compare the safety and effectiveness of percutaneous PNS for the treatment of low back pain to standard interventional management (e.g., radiofrequency ablation, RFA; spinal cord stimulation, SCS, surgery, etc). The treatment of chronic pain in the back is included in the indication statement for SPRINT PNS (K181422, K211801). This study will compare the efficacy of percutaneous PNS for the treatment of chronic low back pain to standard interventional management for the treatment of chronic low back pain, by evaluating if the treatment effect is equivalent (i.e., statistically non-inferior), and if so, if it is superior.

4.2. Subject Population

Prospective subjects will be screened for eligibility into the study using the Eligibility criteria listed in Section 4.2.1.

4.2.1. Selection Criteria

Inclusion Criteria

- Age \geq 21 years and \leq 75 years
- Able to understand and comply with study requirements and provide written informed consent
- Chronic low back pain (*i.e.*, pain lasting longer than 6 months, where the vast majority and center of pain is in the lumbar region, L1-L5 vertebral levels)
- Reports an average low back pain score \geq 4 on a scale of 0-10 (BPI-5)
- Previous use of at least two types of LBP therapies (*e.g.*, medications, physical therapy, injections, etc.)
- At least 4 weeks of stable pain treatment or medication as indicated by subject reported medication history (*i.e.*, no new treatments or change in medication for pain in the last 4 weeks)
- Reports active health insurance coverage (*e.g.*, through commercial insurance, Medicare, Medicaid, Tricare)

Exclusion Criteria

- Radicular leg pain (*e.g.*, pain that spreads to the lower extremities) or referred pain outside the lumbar region (*e.g.*, sacral pain, hip pain) that is \geq 4 on a scale of 0-10, BPI-5
- Pain in the thoracic or cervical region that is \geq 4 on a scale of 0-10, BPI-5
- Pain from the sacroiliac joint, as determined by the Investigator
- Signs of infection on or around the low back, or other conditions that increase risk to the subject in the opinion of the Investigator (*e.g.*, valvular heart disease that creates an infection risk, compromised immune system, history of recurrent skin infections)
- Signs of serious underlying cause of low back pain as determined by the Investigator, (*e.g.*, cancer, chronic infection, referred visceral pain, metabolic bone disorder)
- Deep brain stimulation (DBS) system, an implanted active cardiac implant, or any other implantable neurostimulator whose stimulus current pathway may overlap the Sprint Stimulator's current pathway
- Anesthetic or corticosteroid injections in the low back (including trigger point, epidural, intrathecal, facet, or sacroiliac joint injections) within the last 3 months (not including a diagnostic medial branch block), or botulinum toxin (Botox) injection in the low back within the last 6 months
- Prior radiofrequency ablation of the lumbar medial branches (L1-L5) within the last 6 months
- Prior lumbar surgery
- Clinically relevant stenosis of the central canal or foramina as determined by the Investigator (*e.g.*, symptoms of neurogenic claudication)
- Greater than mild lumbar scoliosis (*i.e.*, $>$ 20 degrees)
- Condition that could impact response to percutaneous PNS (*e.g.*, fibromyalgia confirmed by a specialist, multiple sclerosis, spinal cord injury)
- History of significant trauma to the lumbar spine or paraspinal musculature (*e.g.*, burst fractures or fracture dislocations)
- Score of $>$ 20 on the Beck Depression Inventory (BDI-II)

- Average Pain Interference score < 4 using BPI-9
- Obese with a body mass index (BMI) > 40
- Current illicit substance abuse or high-dose opioid dependence (e.g., daily opioid usage \geq 90 mg morphine equivalents)
- Current participation, or less than 30 days from completing any drug or device trial, or previously received SPRINT for LBP

- Note: subjects in the follow-up phase of a COVID-19 vaccine study will be allowed to participate in this study, provided the vaccine is cleared under a FDA Emergency Use Authorization or full FDA approval.]
- Pending litigation, workers compensation or other secondary gain issues
- Tape or adhesive allergy
- Allergy to all local anesthetic agents (e.g., lidocaine)
- Any other medical condition that may interfere with ability to participate in a clinical trial as determined by the Investigator (e.g., bipolar disorder)
- Vulnerable populations (e.g., prisoners, individuals that report to investigators)
- Bleeding disorder (e.g., hemophilia)
 - Note: anticoagulant use is not considered a bleeding disorder.

Additional Inclusion Criteria (assessed before randomization)

- Average pain intensity score of ≥ 4 (determined by calculating the mean “average pain” collected in a 7-day baseline diary, using Question #5 on the BPI-SF)

Additional Exclusion Criteria (assessed before start of treatment)

- Pregnancy (Group #1 only)

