4.2.6. Sample Size & Justification

Up to 30 sites will participate in the study. The study will be planned with a maximum sample size of 230 enrolled subjects

Subjects will be randomized to either Group #1 or Group #2 using a 1:1 randomization scheme.

All subjects who sign a consent will receive a subject ID number. Subjects who sign a consent and do not meet all study eligibility criteria will be considered screen failures and not count against the number of enrolled subjects. Subjects who are randomized at Visit 2 will be counted as enrolled. If a subject does not receive the randomized intervention (e.g., complete PNS or receive a standard interventional procedure), their results may be excluded and/or analyzed separately from the rest of the population.

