5.2. Visit 2 – Randomization

Visit 2 will be conducted upon completion of the baseline diary. The following measure will be assessed:

- Selected questions from Brief Pain Inventory (BPI) (e.g., BPI-3, BPI-5)

Randomization will occur after the following criterion has been met:

- All subjects must have completed all 7 days of the 7-day baseline diary to be eligible to continue participation in the study. The mean "average pain" (BPI-5) score from this diary will be calculated to confirm eligibility (i.e. "average pain" ≥ 4) prior to randomization. If the calculated mean "average pain" from the first week diary is < 4 , the subject will be considered a screen failure, excluded from the study, and will not proceed with the remainder of the visit or study. The diary may be collected either in-person, by mail/email, or completed electronically. If the diary

is collected electronically or by mail/email, Visit 2 may be completed over the phone.

Subjects who meet this additional inclusion criterion will be considered eligible for the study. Qualifying individuals will be randomized in a 1:1 scheme using block randomization to Group 1 (8 weeks of percutaneous PNS therapy following MBB) or Group 2 (standard interventional management). [REDACTED]

Following randomization and completion of Visit 2, all subjects will return to receive a medial branch block or other diagnostic procedure, as appropriate (named Visit 3), before progressing to receive their randomized treatment at Visit 4 (i.e., either SPRINT PNS lead placement for Group 1 or standard interventional management (e.g., RFA, SCS, surgery, etc.) for Group 2.

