Additionally, for subjects in Group 2, another MBB or other diagnostic procedure may be repeated at a repeat Visit 3, if necessary. The necessity of a second Visit 3 will be determined by the Investigator and/or subject's Insurance, as is required for them to receive the randomized therapy (standard interventional management deemed appropriate by the investigator).

If a subject has previously undergone a diagnostic procedure (e.g., MBB, MRI, SCS trial, etc. within 3 months of the baseline visit, results and information may be collected to serve as diagnostic procedures completed for Visit 3.

Details will be collected regarding the approaches used for the diagnostic procedure(s), as well as outcomes following the procedure(s), including adverse events.

Subjects in Group 2 will continue to participate in the study visits independent of their successful completion of diagnostic procedures and/or standard interventional management. For example, if a subject does not proceed to receive lumbar RFA because they failed their MBB (e.g., had less than 50% response), they may receive other treatments for their low back pain recommended by their physician and continue to participate in study visits. In this case, the subject will still return to the clinic at Visit 4 to discuss alternative standard interventional management approaches, which will be regarded as the start of Treatment.

5.4. Visit 4 – Treatment (PNS Lead Placement or start of treatment with Standard Interventional Management)

GROUP 1 - PNS Lead Placement

Subjects randomized to Group 1 will undergo the following prior to lead placement:

- Women of childbearing age and reproductive potential will have a pregnancy test completed as part of eligibility confirmation before or at Visit 4.

- Subjects taking anticoagulants may have their medication adjusted as determined by the Investigator to prevent potential excessive bleeding.

Participants who are randomized to Group 1 and meet all Eligibility criteria will undergo placement of the percutaneous leads. The following measures may be assessed prior to lead placement:

- Selected questions from Brief Pain Inventory (BPI) (e.g., BPI-3, BPI-5)
[REDACTED]
- Current pain treatments/analgesic usage

Figure 2 shows a magnetic resonance image (MRI) of the spine and paraspinal musculature.

[figure not shown]

Figure 2: Magnetic resonance image (MRI) of lumbar paraspinal musculature, multifidus (MF) and longissimus (LS) (54).

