7.4. Subject Screening and Identification Log

A subject screening log will be completed at the clinical site for all subjects who were considered for the study. Those individuals who are excluded will be listed along with the reason for exclusion. Any subject who signs an Informed Consent and does not proceed with procedures associated with treatment or fails to meet eligibility (e.g., baseline diary back pain score < 4) will be considered a screen failure. The Subject Identification log will be completed for subjects enrolled in the study.

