7.5. Subject Numbering

Screened and consented consecutive subjects will be given a unique Subject ID number. Subjects who sign consent and do not meet all study eligibility criteria will be considered screen failures and not count against the number of enrolled subjects. Subjects who are randomized at Visit 2 will be counted as enrolled. A number will be assigned consecutively to each subject at each clinical site. A master list linking the subjects to the unique "Subject ID" numbers will be kept by the study staff in a secure location.

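### Section 7.4 can turn a randomized subject into a screen failure, contradicting 4.2.6 and 7.5, and 4.2.6 leaves open whether untreated randomized subjects are analysed

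*Protocol*

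**What the plan says.** Section 5.2 (Visit 2) treats eligibility as settled once the 7-day diary criterion is met: "Subjects who meet this additional inclusion criterion will be considered eligible for the study". Allocation follows at the same visit: "Qualifying individuals will be randomized in a 1:1 scheme using block randomization".

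Section 4.2.1 then has a further block headed "Additional Exclusion Criteria (assessed before start of treatment"), whose single entry is "Pregnancy (Group #1 only"). Section 5.4 places the pregnancy test before or at Visit 4, among the steps for subjects already randomized to Group 1, and makes lead placement conditional: "Participants who are randomized to Group 1 and meet all Eligibility criteria will undergo placement of the percutaneous leads".

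Four rules bear on what happens to such a subject:

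- Section 7.4 defines a screen failure as "Any subject who signs an Informed Consent and does not proceed with procedures associated with treatment or fails to meet eligibility". The sentence does not stop at randomization.
- Sections 4.2.6 and 7.5 say that consented subjects who do not meet all eligibility criteria are screen failures outside the enrolled count.
- The same two sections say: "Subjects who are randomized at Visit 2 will be counted as enrolled".
- Section 4.2.6 adds that, for a subject who did not receive the randomized intervention, results may be dropped or analysed apart from the others. Its examples cover both arms: completing PNS, and receiving a standard interventional procedure.

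On follow-up, section 5.4 expressly keeps untreated Group 2 subjects in the visit schedule, and section 8.1 says that subjects in either group may continue.

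**The concern.** The primary endpoint (4.3.1.1) compares the proportions with at least 50% pain reduction at 3 months, first for non-inferiority and then for superiority. Randomization protects that comparison only if membership of each group is fixed at Visit 2. Here one criterion is applied after allocation is known and in one arm only. The screen-failure definition is wide enough to reach randomized subjects, and the sentence on analysis membership is discretionary.

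A subject who never starts treatment is unlikely to be a random draw from the group. Removing such subjects changes the denominator, and if removal differs between arms it changes the difference. The discretion also sits beside section 5.11, under which results are reviewed as subjects complete the study.

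**Working it through.** **Step 1: trace one subject through the text.** Take a woman who meets the diary criterion, is randomized at Visit 2 and has a positive test before Visit 4.

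| Rule | If allocated to Group 1 | If allocated to Group 2 |
|---|---|---|
| 4.2.1, additional exclusion | excluded | does not apply |
| 5.4, eligibility condition | no lead placement | does not apply |
| 7.4 | screen failure | not a screen failure on this ground |
| 4.2.6 and 7.5, ineligible subjects | screen failure, not counted | does not apply |
| 4.2.6 and 7.5, randomized at Visit 2 | enrolled, counted | enrolled, counted |

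In Group 1 she is both enrolled and not enrolled, and no visible passage says which rule prevails. The clause in 7.4 on not proceeding with treatment procedures creates the same clash for any subject, in either arm, who is randomized at Visit 2 and untreated at Visit 4.

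**Step 2: group size.** Section 4.2.6: "The study will be planned with a maximum sample size of 230 enrolled subjects". At 1:1 this is 230 / 2 = 115 per group. The 230 itself cannot be reproduced, because no margin, alpha, power or success rate is visible. That is not a criticism here.

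**Step 3: shift in a proportion.** Let n = 115 be randomized to a group, k removed, p the success rate among the rest and q the rate among those removed. Then:

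- kept: [p(n − k) + qk] / n
- removed: p
- shift: (k/n)(p − q)

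With q = 0 (removed subjects would have counted as non-successes) and p assumed at 40%, 50% and 60%:

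| k | k/n | p = 40% | p = 50% | p = 60% |
|---|---|---|---|---|
| 2 | 1.7% | 0.7 points | 0.9 | 1.0 |
| 6 | 5.2% | 2.1 | 2.6 | 3.1 |
| 12 | 10.4% | 4.2 | 5.2 | 6.3 |

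If those removed have some success the shift is smaller. With 10% removed, p = 45% and q = 10%, the kept rate is 0.9 × 45% + 0.1 × 10% = 41.5%, a shift of 3.5 points. If q = p the shift is nil.

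**Step 4: effect on the non-inferiority test.** Assume one-sided alpha 0.025, a margin M of 10 or 15 points, a control rate c of 40–60%, and a true difference among all randomized subjects exactly at the margin. Remove k non-successes from Group 1 only:

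- rate after removal: r = (c − M) × n / (n − k)
- SE = √[c(1 − c)/n + r(1 − r)/(n − k)]
- error = 1 − Φ(1.960 − (r − c + M)/SE)

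Example with c = 0.50, M = 0.10, k = 12: r = 0.40 × 115/103 = 0.4466; SE = 0.0676; (0.4466 − 0.50 + 0.10)/0.0676 = 0.689; error = 1 − Φ(1.271) = 0.102.

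Across the assumed rates and margins the error is 0.030–0.034 for k = 2, 0.041–0.061 for k = 6 and 0.067–0.138 for k = 12. Removing non-successes from Group 2 instead would raise the control proportion and push the comparison the other way.

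**The case against.** The best defence is that 7.4 concerns a screening log. Its example of failed eligibility is a baseline diary score below 4, a check made before randomization; enrolled subjects have a separate log; and the rule that randomized means enrolled appears twice. On that reading 7.4 is only loosely worded, and a log label does not define an analysis set. Analysis sets are commonly left to the SAP, which was not available for this point. Section 4.2.4 (Subject Disposition) is listed in the contents but its body is not visible, and it might settle the matter.

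Much of this is fair. The log reading is plausible, but the clause on not proceeding with treatment describes something that happens at Visit 4, after randomization, and so cannot be confined to screening without an edit. The sentence in 4.2.6 concerns results rather than logs, so the question of analysis membership does arise in the protocol itself. A SAP or a hidden section could choose between the rules, but the visible sections would still conflict.

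A reader might go further and infer that removal would in practice fall on Group 1 alone. The documents do not support that. Section 8.1 lets subjects in either group continue, 5.9 keeps Group 1 subjects who decline further leads in follow-up, 5.12 keeps Group 1 subjects who take other treatments, and the option in 4.2.6 names both arms. Section 5.4 is more explicit about retaining untreated Group 2 subjects, so unequal handling is possible, but neither its presence nor its direction is established.

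**Conclusion.** The contradiction is real: 7.4 conflicts with the rule in 4.2.6 and 7.5 that everyone randomized is enrolled, and the Group 1-only criterion assessed after allocation gives a concrete case that meets both definitions. With the exclusion option in 4.2.6, the text permits removal after randomization from the primary comparison. It does not show that such removal will happen, so a reader should not conclude that the randomized groups are certain to be lost.

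The size rests entirely on assumed rates. Pregnancy alone would probably involve few subjects, and two would mean about 1 point. If non-treatment reached 12 of 115 in one arm and all were non-successes, the shift would be 4–6 points. The protocol should be corrected, since the change is small and the primary comparison depends on it.

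**What to change.** 1. In 7.4, limit screen failure to subjects not yet randomized, and align the matching sentences in 4.2.6 and 7.5.
2. In 4.2.6, replace the exclusion option, as far as the primary comparison is concerned, with a statement that every randomized subject is analysed in the randomized group. Keep as-treated results as supportive, and report reasons for non-treatment by group.
3. State that the result of the pre-placement pregnancy check, whatever it means for treatment, does not alter analysis membership.
4. Optionally, where feasible, assess the pregnancy criterion for all subjects before randomization and leave the pre-placement check as it is. This would make eligibility independent of allocation, but items 1–3 do not depend on it.

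Items 1–3 are wording changes. Item 4 adds a test for the women concerned in Group 2 and perhaps a few exclusions before randomization. The statistical cost is that untreated subjects may slightly dilute the observed PNS success rate. Where untreated subjects in both arms fare alike, the difference also shrinks towards zero, which can favour non-inferiority. An as-treated or per-protocol result should therefore be reported alongside the primary one.
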